3.2 Treatment failures and/or inadequate response

Patients who have not had an adequate response to the ACTH treatment after 14 days may either be given a choice of getting another round of ACTH for additional 10 days or switching to IV Methylprednisolone 1000 mg for 3 days. The scheduling of blood draws and MRIs will not be affected and continue as planed.

3.3 Concomitant disease modifying therapies (DMTs)

Patients undergoing relapses will continue their current DMTs during the relapse. One month after the relapse (after the 1 month MRI time point and blood draw), physician and patient will decide whether to continue their current DMT over time or switch to another DMT. All DMTs and other symptomatic treatments will be recorded during the course of the study.

3.4 Statistical Analysis

All data collected will be documented using summary tables, figures, and patient data listings. For longitudinal data, mixed effects regression model will be used to summarize patterns over the one-year period. All hypothesis testing will be at the 0.05 level of significance. Correlation analyses between specific measures will be accomplished using Pearson's correlation co-efficient.

All summary statistics will be displayed as a function of study visit or assessment time. Summary statistics for continuous variables will include n, mean, standard deviation, minimum, median, and maximum. For categorical variables, frequencies and percentages will be presented. Graphical displays will be provided as appropriate.

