1.3 MRI Assessments

All images will be performed at the University of Chicago's Magnetic Resonance Imaging Research Center (MRIRC). The MRIRC is fully dedicated to MRI research and located in the Q300 suite in the Department of Radiology of the University of Chicago Medical Center. The MRIRC houses two state of the art MRI scanners and is staffed by 2 full-time MRI technologists, research nurses, and coordinators. [name] has over 20 years' experience in neurological imaging and is the Director of Neuroimaging for the MRIRC and will oversee all aspects of imaging.

The primary outcome of all MRI techniques is to determine whether there is an improvement and subsequent stabilization/repair over time of tissue damage caused by inflammatory MS disease activity. Multiple conventional and nonconventional MR imaging modalities are examined here to determine which of these are the most sensitive and reliable in detecting microstructural damage and repair over time. The results of this study will also greatly impact the design of future MS trials by providing a guide for selecting the most appropriate MRI and immune methods to assess treatment efficacy in MS.

Conventional MRI

Quantitative T1 Gd+, T2, T1 chronic, and BPF analysis:

Commonly used MRI metrics in most studies include a post-contrast T1 weighted sequence and a T2 weighted sequence. These are useful for detecting new inflammatory lesions. The contrast-enhancing lesions are transient (less than 2 months on average) and are indicative of active lesions. The T2 lesions are more permanent and are thought to develop after enhancement ceases. Measurement of lesion load in terms of number and volume, both active and inactive (T1 Gd+, T2 chronic lesions, and T1 chronic lesions) will be examined over time.

Specific Aim: determine the effects of ACTHAR in improving the characteristics of contrast enhancing lesions (T1 Gd+) observed at baseline and followed squentially over time to the development of T2 and chronic T1 signal intensities.

Quantitative nonconventional MRIs (see Supplement for protocol details):

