- 1. **Aim1**. Determine immune subset expression in CD4+FOXP3 Tregs and CD8+CD28- T suppressor cells by flow cytometry at each visit above.
- 2. **Aim 2**. Determine global gene expression profiling in MNC with 913,000 probes at each visit above. Bioinformatics will include pathway analysis and ACTHAR-induced RNA signature.
- 3. **Aim 3**. Determine serum protein profiling for immune-regulated cytokines (Th1, Th2, Th17, monokines...) and neuroprotective proteins (NGF, BDNF, ACTH, HGF, CNTF, IL-10...) at each visit above.

4. **Aim 4.** All data from protein and gene expression, as well as immune subset expression will be compared to our database generated from therapy-naïve stable and exacerbating MS. ACTHAR signature will analyzed based on these comparisons.

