2.5 Methods

Blood is drawn from 18 MS patients at baseline, last day of ACTHAR (day 10 of therapy), 1 month post 1st dose, and months 3 and 6. Mononuclear cells (MNCs) from four 8cc heparin green-top tubes (40-60 million cells) are separated on Ficoll-Paque gradients. 30M cells are needed for flow cytometry. 20M cells are needed for total RNA preparation.

Specific Aim 1. Determination of ACTHAR effects on immune cell subsets in relapsing remitting MS (RRMS), emphasizing expression on CD8 cells including the CD8+CD28-regulatory subset. Flow cytometry will be conducted to determine the effect of ACTHAR on in vivo expression of surface markers on T cells (CD4, CD8, CD28, FOXP3). Reagents are from e-Biosciences and B-D. (MAbs = CD4, CD8, CD28, CD27, CD25, FOXP3).

Specific Aim 2. Global gene expression profiling in MNC will be measured with 913,000 probes at each sample. Bioinformatics will include pathway analysis and ACTHAR-induced RNA signature. Total RNA will be isolated from 20M cells, as the template for synthesizing cDNA for gene expression array analysis with Affy HTA kit. RT-PCR will be performed for validation of specific gene signatures.

Specific Aim 3. Serum from each sample will be applied on Procarta multiplex assay plates according to manufacturer's instruction. Immune, neuroprotection, and other proteins will be measured with 40 highly-selected targeted antibodies for Th1, Th2, Th17, monocyte, neuroprotection, cell proliferation and death, and adhesion molecule panels.

Specific Aim 4. Advanced bioinformatics with Gene Set Variation Analysis:

- 1. Identify differential gene expression (DEG) between groups;
- 2. Analyze pathways by Ingenuity Pathway Analysis (IPA);
- 3. Discover transcriptional signature of genes and gene pathways;

4. Build a predictive model using machine learning algorithms including Random Forests (RFs) and Support Vector Machines (SVMs).

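### Section 3.4 sets all testing at 0.05, and nothing in the plan gives a multiplicity rule for the gene, gene-set and 40-protein analyses

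*Combined protocol and SAP*

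**What the plan says.** Section 3.4 is the only statistical section and gives the only significance level: "All hypothesis testing will be at the 0.05 level of significance". It does not say whether tests are one- or two-sided, or whether the level applies to raw or adjusted p-values. The same section says that for longitudinal data a "mixed effects regression model will be used to summarize patterns over the one-year period".

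The immune part plans analyses with very many outcomes. Under Specific Aim 2 of section 2.5, "Global gene expression profiling in MNC will be measured with 913,000 probes at each sample". Under Specific Aim 3, "Immune, neuroprotection, and other proteins will be measured with 40 highly-selected targeted antibodies". Specific Aim 4 is headed "Advanced bioinformatics with Gene Set Variation Analysis", and its first step is "Identify differential gene expression (DEG) between groups", followed by pathway analysis, a transcriptional signature and machine-learning models. Aim 4 in section 2.4 adds an external comparison: "All data from protein and gene expression, as well as immune subset expression will be compared to our database", which holds therapy-naive stable and exacerbating MS. RT-PCR validation of specific signatures is planned under Specific Aim 2. None of these sections states an FDR, a family-wise method, a testing hierarchy or a threshold of its own.

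**The concern.** A flat 0.05 does little harm to a handful of tests. It behaves very differently over tens of thousands of transcripts or 40 proteins, because the expected number of chance findings grows in proportion to the number of tests. The RNA signature and the protein profile are planned products of the study, and section 2.6 puts RNA and serum proteins forward as possible efficacy biomarkers. If entries are declared at unadjusted p < 0.05, a reader cannot judge how many of them are chance.

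The planned features do not close the gap. Gene-set and pathway methods cut the number of tests, but no threshold is given for the set tests either. RT-PCR can confirm that a transcript was measured correctly. No independent sample is described for it, so it does not control false selection.

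**Working it through.** **Nothing to reproduce.** The 0.05 level is stipulated, and the sample size of 18 (section 3.1a) carries no effect size, SD or power. The check is therefore what the rule implies if followed literally.

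**Inputs from the plan.** Level 0.05 (section 3.4); 40 proteins and 913,000 probes (section 2.5); 18 patients; five immune samplings, hence four post-baseline contrasts (section 2.4).

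**Assumed inputs, not in the plan.** m = 20,000 to 70,000 summarised gene features, or 1,000 to 5,000 gene sets; c = 500 or 5,000 truly changed features; power 50% or 80%; correlation 0.5 between proteins as an alternative to independence.

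**Step 1: genes, one contrast, no true change.** Expected chance declarations = 0.05 × m, whatever the correlation.
- 0.05 × 20,000 = 1,000; 0.05 × 70,000 = 3,500
- Gene sets: 0.05 × 1,000 = 50; 0.05 × 5,000 = 250

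**Step 2: proteins, one contrast, no true change.**
- Expected: 0.05 × 40 = 2
- At least one, independence: 1 − 0.95^40 = 0.871
- At least one, equal correlation 0.5 (simulated normal statistics, two-sided): 0.572
- Over four post-baseline contrasts: 0.05 × 160 = 8 expected

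**Step 3: false share of the gene list when some effects are real.** Share = 0.05(m − c) / [0.05(m − c) + power × c].

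| m | c | Power | False / all declared | Share |
|---|---|---|---|---|
| 20,000 | 500 | 50% | 975 / 1,225 | 80% |
| 20,000 | 500 | 80% | 975 / 1,375 | 71% |
| 20,000 | 5,000 | 50% | 750 / 3,250 | 23% |
| 20,000 | 5,000 | 80% | 750 / 4,750 | 16% |
| 70,000 | 500 | 50% | 3,475 / 3,725 | 93% |
| 70,000 | 500 | 80% | 3,475 / 3,875 | 90% |
| 70,000 | 5,000 | 50% | 3,250 / 5,750 | 57% |
| 70,000 | 5,000 | 80% | 3,250 / 7,250 | 45% |

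The range is 16% to 93% overall, and 16% to 57% where 5,000 features change.

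**Step 4: what FDR control would cost.** Simulated paired t-tests, 18 patients, 20,000 independent features, 40 runs per case, Benjamini-Hochberg at 5%:

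| Truly changed | Declared at 0.05 (false) | Declared at FDR 5% (false) |
|---|---|---|
| 500 by 0.70 SD | 1,374 (972) | 27 (1 to 2) |
| 5,000 by 0.70 SD | 4,751 (754) | 2,391 (91) |
| 500 by 1.2 SD | 1,467 (968) | 444 (22) |

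In the first case the 0.05 list holds 1,374 − 972 = 402 real features, against about 25 under FDR control.

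**The case against.** The strongest reply has four parts.

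**Scope of section 3.4.** It names neither genes nor proteins. Its model sentence refers to one year, which fits the MRI schedule, while immune sampling ends at month 6. It is also silent on raw versus adjusted p-values. A reader might infer that the plan prescribes uncorrected gene testing; the text does not go that far. What stands is that the only written rule covers all testing, and nothing exempts the immune data or says how p-values are adjusted.

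**Size.** A reader might multiply 913,000 probes by 0.05 and report 45,650 false findings. That needs a separate test on each probe, which is not the natural reading of a differential-gene and gene-set analysis; it is at most an upper bound. A reader might also infer that most of the signature would be false. More than half is false in 5 of the 8 cases above, but that count reflects the chosen grid, not a likelihood. The only count of changed genes in the document is 5,000, in a figure caption in section 2.1. It comes from earlier data, with broken text and no stated threshold, so it cannot settle the matter. It does match the more favourable rows.

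**Purpose.** This is an 18-patient, single-group, mechanistic study, and strict control can discard many real signals, as step 4 shows. That cost is genuine and lowers the severity. It argues for choosing the FDR level with care and publishing full rankings, not for leaving the rule unwritten. Only oxygen extraction fraction is labelled exploratory (Supplement).

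**MRI.** A reader might extend the same criticism to the imaging, since section 1.3 says "The primary outcome of all MRI techniques is to determine whether there is an improvement and subsequent stabilization/repair over time of tissue damage". However, the technique-level aims do name metrics and often lesion types. What is missing is a primary choice among them, and a visit. Section 1.3 also sets out to compare modalities, so a single primary metric would be a trade-off rather than a correction.

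**Conclusion.** The concern holds as a should-fix point about the gene, gene-set and protein analyses. The omission is certain from the text: one level for all testing, and no multiplicity rule anywhere. The protein figures (about 2 of 40 by chance; 57% to 87% chance of at least one) rest on the plan's own count, no true change, and the stated correlation range. The gene figures rest on assumed feature counts, numbers of changed features and power, so they show what the literal rule allows and do not forecast this trial's list.

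The documents do not support rating this as a fatal flaw, claiming that most of the signature will be false, or treating the MRI plan as equally deficient. Nor would error control separate a drug effect from natural recovery in a single-arm study. Section 1.3 itself describes enhancing lesions as transient and expects myelin water fraction to improve as lesions repair.

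**What to change.** Keep the 0.05 sentence in section 3.4, because the flow-cytometry subsets, the Pearson correlations and the MRI analyses would otherwise have no significance level. Add after it:

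*Exceptions: transcripts or gene sets are declared at Benjamini-Hochberg FDR 5% across all tested features within each pre-stated contrast, and serum proteins at Benjamini-Hochberg FDR 5% across the 40 proteins within each contrast. Full ranked estimates are also reported as exploratory.*

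The contrasts must be listed for this to work. The sponsor may fix another FDR level, but before results are seen.

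The change needs SAP wording and routine code; no patient, visit or assay is affected. The real cost is shorter lists, severe if effects are few and moderate and much milder if they are many or large (step 4).

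A separate, optional MRI note: the sponsor may name one primary metric and one contrast or visit. Otherwise, MRI results should be reported as estimates with 95% confidence intervals and described as exploratory.

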Effects of ACTHAR on Advanced MRI Surrogate Markers of Disease Activity and on Comprehensive Immune Signature During MS Relapses IRB16-1390 NCT3021317 Protocol Date 10/23/19

Effects of ACTHAR on advanced MRI surrogate markers of disease activity and on comprehensive immune signature during MS relapses

This investigator-initiated trial (IST) is divided into two complementary parts:

- Advanced serial MRI studies on patients during and after an acute MS relapse. MRI will be performed at baseline, 1 month after the 1st dose of ACTHAR, and months 3, 6, and 12. ACTHAR will be administered for 10 days. Patients will start ACTHAR within 48 hours of relapse assessment.
- Serial immune assays on patients during and after an acute MS relapse. Serum and blood samples with be collected at baseline, last day of ACTHAR (day 10 of therapy), 1 month post 1st dose, and months 3 and 6.

ACTHAR will be administered by a self-injectable syringe under the skin fat tissue (subcutaneous injection). The first subcutaneous injection of ACTHAR will be done in the clinic. Subjects will undergo a teaching session with the PI ([name]) about how to give a subcutaneous injection of ACTHAR. All subsequent injections will be self-administered by the patient.

At each research visit, subjects will have a physical/neurological examination, blood pressure, height, weight, and temperature taken at the time of visits. Urine pregnancy test or urine analysis may be done if there is a clinical concern for pregnancy or urine infection. This will be based on the discretion of the investigators.

Part I. Investigational Plan-MRI

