2.6 Outcomes

This data may lead to better understanding of the mechanism of action of ACTHAR and identifying signatures/biomarkers in ACTHAR-treated MS. In addition, MRI, CD8+CD28- cell numbers, serum proteins, and RNA may be biomarkers for efficacy.

Part III. Patient criteria and publications

3.1a Inclusion Criteria

This study will be restricted to adult patients (>18 years) undergoing a clinical relapse who also must have a contrast-enhancing CNS lesion, either clinically or non-clinically relevant. Sample size under consideration is 18 patients. The population on which analyses will be conducted consists of all patients who have received at least 1 dose of study medication and for whom at least two time-points (baseline and at least one additional time-point) for MRI data are available (Intent-to-treat analysis).

3.1b Exclusion Criteria

1-Patients will be excluded if they only have a clinical relapse which is not associated with MRI findings of a new or enlarging MS lesion.

2-Patient will be excluded if they cannot give written consent

3-Patients will be excluded if they have an active infection

4-Patients will be excluded if they already received steroids (IV or oral) within last 30 days of receiving ACTHAR

5-Pregnant or lactating patients will be excluded from this study.

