Whole brain isotropic voxel size mcDESPOT imaging will be acquired using the following imaging parameters: FOV = 22 cm, matrix = 128 × 128, slice thickness = 2 mm; SPGR parameters: echo time/repetition time (TE/TR) = 2.1/6.7 ms, flip angle (α)=[3,4, 5, 6, 7, 8, 11, 13, 18]°; bSSFP parameters: TE/TR = 1.8/3.6 ms, α = [11, 14, 20, 24, 28, 34, 41, 51, 67]°, two phase cycles acquired per bSSFP flip angle. The total mcDESPOT acquisition time is ~13 min ¹³.

Magnetization transfer imaging (MTI): this imaging technique interrogates the transfer of magnetization (MT) from protons bound to macromolecules to more mobile water associated protons. This MT effect is quantified by acquiring two images, one with and the other without a resonance pulse. MTI will be performed using 2D gradient echo (GE) sequence (TR=640, TE=12, FA 20°) with and without an off resonance radiofrequency (RF) saturation pulse (off frequency=1.5 kHz, Gaussian envelope duration 7.68ms, FA=500°).

MTR=(Moff - Mon)/Moff.

MTR of the active and inactive lesions as well as normal appearing white and gray matter will be determined. MTR of the lesions will be determined by the region of interest (ROI) analysis.

Diffusion Tensor Imaging (DTI): images will be acquired using single shot spin-echo planar pulse sequence TR= 7658 ms, TE= 70 ms, matrix size = 128 x 128, FOV = 224 x 224 with diffusion gradients (b-value =800 s/mm²) applied in 32 noncollinear directions. Fractional Anisotropy, mean diffusivity, radial ($\lambda \perp$) and axial (λ II) diffusivities of active and chronic lesions will be determined by ROI analysis.

References:

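### Plain Pearson correlation is the only method named for relating measures that are repeated over visits and lesions in 18 patients, and the unit of analysis is left open

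*Combined protocol and SAP*

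**What the plan says.** Section 3.4 (Statistical Analysis) assigns methods in three sentences.

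- Time patterns: "For longitudinal data, mixed effects regression model will be used to summarize patterns over the one-year period".
- Testing: "All hypothesis testing will be at the 0.05 level of significance".
- Association: "Correlation analyses between specific measures will be accomplished using Pearson's correlation co-efficient".

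The mixed model is given for describing change over the year, not for relating one measure to another. The association sentence does not name the measures, the visit or change score, or the unit. It gives no method for repeats and no transformation or rank alternative. The bioinformatics listed in section 2.5 concern gene signatures and prediction and do not fill this gap.

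The data are clustered at two levels.

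- Visits: "MRI will be performed at baseline, 1 month after the 1st dose of ACTHAR, and months 3, 6, and 12" (introduction). Blood is taken at baseline and then "last day of ACTHAR (day 10 of therapy), 1 month post 1st dose, and months 3 and 6". Each series has five visits. They share four: baseline and months 1, 3 and 6.
- Lesions: "MTR of the lesions will be determined by the region of interest (ROI) analysis" (Supplement, magnetization transfer imaging). The DTI paragraph treats active and chronic lesions in the same way. Section 1.3 adds "Measurement of lesion load in terms of number and volume".

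On size, section 3.1a says "Sample size under consideration is 18 patients".

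**The concern.** The usual test of Pearson's coefficient treats every point as independent. Visits within a patient, and lesions within a patient, are not independent. If 18 patients at four or five visits are entered as 72 or 90 points, the test claims more information than exists, and unrelated measures will look linked too often.

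The alternative, one value per patient at one visit, is valid. But it discards the within-patient change that a serial design is meant to capture, and it leaves only 18 points. Where a measure is strongly skewed, a few patients can dominate the coefficient.

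Because the sentence permits several analyses, the choice among them could be made after seeing the data. What is at stake is how MRI-MRI, immune-immune and MRI-immune associations are interpreted.

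**Working it through.** The plan states no target correlation, power or variance, so there is no figure of its own to reproduce.

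**Inputs from the documents.** 18 patients; 5 MRI visits; 5 blood visits; 4 shared; level 0.05 (taken as two-sided).

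**Assumed inputs, because the documents give none.** Intraclass correlation (ICC) 0 to 0.9, equal in both measures; 2 to 5 lesions per patient; lognormal sigma 0.5 to 1.5 for skewed measures.

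**1. Visits pooled, no true association.** With v visits and the same ICC in both measures, the variance of r is inflated by about D = 1 + (v − 1) × ICC². The actual error rate is then roughly 2Φ(−1.96/√D). For v = 4 and ICC 0.5, D = 1 + 3 × 0.25 = 1.75, and 2Φ(−1.96/1.323) = 2Φ(−1.48) ≈ 14%. Monte Carlo runs give the rates directly; where two sets of runs differ by a point, both values are shown.

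| ICC | D, 4 visits | Type I error, 4 visits (72 points) | D, 5 visits | Type I error, 5 visits (90 points) |
|---|---|---|---|---|
| 0 | 1.00 | 5% | 1.00 | 5% |
| 0.3 | 1.27 | 8% | 1.36 | 9% |
| 0.5 | 1.75 | 13–14% | 2.00 | 16% |
| 0.7 | 2.47 | 22% | 2.96 | 26% |
| 0.9 | 3.43 | 30–31% | 4.24 | 36–37% |

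The four-visit column applies to MRI-immune pairs. The five-visit column applies to MRI-MRI or immune-immune pairs.

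**2. Lesions pooled.** Four lesions per patient at one visit give 8% to 14% at ICC 0.3 to 0.5. Lesions and five visits pooled together give 14% to 36% with two lesions per patient and 20% to 44% with five, when patient and lesion effects together make up 0.4 to 0.8 of the variance.

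**3. One value per patient.** Type I error stays at 5%. With t = 2.120 on 16 df, the critical |r| is 2.120/√(16 + 2.120²) = 0.468. For 80% power the true r must be about tanh((1.960 + 0.842)/√15) = 0.62. Fisher-z power is 22%, 38% and 57% at r = 0.3, 0.4 and 0.5. Averaging visits does not change this materially (simulated 23%, 39–40% and 58–59%, against 23%, 39% and 59% for a single visit).

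**4. Within-patient (repeated-measures) correlation.** Type I error is 4.9% to 5.4% at every ICC tried. With 18 × 5 complete observations, power is about 74%, 95% and over 99% at a within-patient r of 0.3, 0.4 and 0.5.

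**5. Skewness, n = 18, both measures lognormal.** At latent r = 0.6, Pearson on raw values has power of 58–59% (sigma 1.0) and 50% (sigma 1.5). Spearman has 71–72% and Pearson on logs 79%. At sigma 0.5 (run at latent r = 0.5), Pearson and Spearman are equal at about 52%. With no association, raw Pearson rejects 4.9% to 6.6% of the time, so skewness mainly costs power. The false-positive argument rests on clustering.

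**The case against.** The strongest reply is that the plan never pools anything. Section 3.4 displays summary statistics by visit, and a by-visit Pearson on 18 values is at least as natural a reading; on it, each test holds its 5% level. This stands. A reader might infer from the table above that the trial's correlations will carry false-positive rates of 30% or more, but the documents do not support that. The defect is that the sentence leaves the unit open.

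A reader might also infer that MRI-immune correlations are the planned route to naming biomarkers. The documents do not say so. Section 2.6 says only that MRI, cell numbers, proteins and RNA are possible efficacy biomarkers. The signatures in sections 2.4 and 2.5 come from differential expression, pathway analysis, machine learning and comparison with an existing database. No specific aim is stated as a correlation.

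Two further complaints are not faults of Pearson. Testing each visit separately gives about an 18% (four visits) or 21% (five visits) chance of at least one p < 0.05 at ICC 0.5, but Spearman would share that multiplicity. Low power with one value per patient comes from n = 18, and the cross-sectional part of the fix keeps that limit.

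Finally, skewness of lesion counts, volumes and cytokines is plausible but undocumented, and nothing suggests that MTR or the diffusivities are skewed.

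What remains is that a method is named, it does not suit repeated and nested data, and nothing else in the plan supplies one that does.

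**Conclusion.** The point holds in a limited form. Plain Pearson is the only stated method for association, the data are repeated over visits and lesions, and the mixed model is not assigned to this task. If visits were pooled, the error rate at nominal 5% would be about 8% to 31% for MRI-immune pairs and 9% to 37% for five-visit pairs over ICC 0.3 to 0.9. It would be nominal at ICC 0. These sizes rest on assumed ICCs and on clustering in both measures. The power loss from skewness needs strong skewness (sigma 1.0 or more) and disappears against Spearman at sigma 0.5.

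The correlations appear secondary or exploratory. The effect is on how associations are read, not on the main longitudinal analysis, so this should be corrected but does not undermine the study.

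**What to change.** Replace the sentence in section 3.4 with text that does the following.

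- Names the pairs of measures, and the visit or change score for each.
- **Longitudinal associations:** uses a repeated-measures correlation, or a mixed model of one measure on the within-patient deviation of the other, with random effects for patient (and lesion where lesions are the unit) and visit as a fixed effect. The plan should say which. A plain repeated-measures correlation does not remove a time course common to all patients; the model with visit does.
- **Cross-sectional associations:** uses one value per patient, with lesions averaged within patient, at one named visit or on change from baseline. Skewed measures are log-transformed or analysed by Spearman's rank correlation, with the choice stated in advance.

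The cost is SAP wording, with no new patients, visits or assays. Intervals will be wider than from a pooled Pearson analysis. The power gain of the repeated-measures approach applies only to associations that exist within patients and needs reasonably complete visits. A purely between-patient association still rests on 18 independent units.
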